6. GENERAL ANALYSIS DEFINITIONS

6.1 TREATMENTS

For basic study information on treatments to be administered, assignment of treatment groups, and selection of doses, cf. Section 4 of the CTP.

Each subject is planned to be treated in two subsequent treatment periods. In the first treatment period, subjects will receive a single dose of 25 mg of BI 425809 (reference treatment, R). In the second treatment period, subjects will receive treatment with rifampicin 600 mg once daily over 10 days together with an administration of a single dose of 25 mg of BI 425809 on the seventh day of rifampicin treatment (test treatment, T). The sequence of these treatment periods is fixed and the same for all subjects.

For statistical analyses of AEs, laboratory tests, and vital signs, the following separate analysis phases will be defined for each subject:

Table 6.1: 1 Flow chart of analysis phases for statistical analysis of AEs, safety laboratory and vital signs

Study analysis phase	Label	Start	End
Screening	Screening	Date of informed consent at 12 a.m.	Date/time of first administration of BI 425809
On treatment BI 425809	BI 425809	Date/time of first administration of BI 425809	Minimum of date/time of first administration of BI 425809 + REP (11 days * 24 h) and first administration of loading RI
Follow-up BI 425809 ¹	F/U BI	Date/time of first administration of BI 425809 + REP (11 days * 24 h)	Date/time of first administration of loading RI
On treatment RI	Loading RI	Date/time of first administration of loading RI	Date/time of second administration of BI 425809
On treatment BI 425809+RI	BI 425809+RI	Date/time of second administration of BI 425809	Date/time of second administration of BI 425809 + REP (11 days * 24 h) or 12:00 a.m. on day after trial completion date, whichever occurs earlier
Follow-up BI 425809+RI ¹	F/U BI+RI	Date/time of second administration of BI 425809 + REP (11 days * 24 h)	12:00 a.m. on day after trial completion date
Post study ²	Post-study	12:00 a.m. on day after trial completion date	Not defined – a placeholder date is used, e.g. a date after database lock

¹ Follow-up phases might not exist, e.g. if loading RI is administered within 11 days of the time of administration of BI 425809, or the trial completion date is within 10 days of the time of administration of BI 425809+RI.

² AE tables will present results for the post-study phase only if at least one AE occurred in the post-study phase.

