CTR Section 15, Appendix 16.1.9.2.8.2 and Appendix 16.1.9.2.8.3 AE displays will present results for the following study treatments during on-treatment phases:

- BI 425809
- Loading RI
- BI 425809+RI

Screening, follow-up and post-study periods will not be included in these sections/appendices.

In CTR Section 15 AE tables (but not in Appendix 16.1.9.2.8.2 and Appendix 16.1.9.2.8.3 AE tables), the following totals will be provided in addition:

- a total over the on-treatment phases of "BI 425809" and "BI 425809+RI" ("**Total BI**")
- a total over all on-treatment phases included in this analysis ("**Total on treatment**"). This includes all BI treatments and loading RI.

CTR Appendix 16.1.9.2.8.1 displays will present results for the screening, on-treatment, follow-up and post-study phases (post-study only if at least one AE occurred in the post-study phase).

Additionally to the totals defined above, the following total will be provided in CTR Section 16.1.9.2.8.1 AE tables:

- a total over all study phases ("**Total**")

Laboratory analyses will present results by treatment period (i.e., for treatment periods "BI 425809", "BI 425809+RI", and "Loading RI" plus "BI 425809+RI").

Analyses of vital signs will present results by BI 425809 treatment periods (i.e., for treatment periods "BI 425809", and "BI 425809+RI").

More details on the technical implementation of these analyses are provided in the ADS Plan of this TSAP.

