6.7 BASELINE, TIME WINDOWS AND CALCULATED VISITS

Baseline for the evaluation of data of the “BI 425809+RI” treatment period will be defined as the last available value at Visit 3 before the second BI 425809 dose.

For an additional laboratory summary, baseline of treatment period 2 (“Loading RI” plus “BI 425809+RI”) is defined as the last follow-up assessment during treatment period 1 (i.e., lab value at Day 43).

Time windows are defined in Section 6.1 of the CTP. Adherence to time windows will be checked at the RPM/DBLM.

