The frequency of subjects with AEs will be summarised by treatment, primary system organ class and preferred term. AEs which were considered by the investigator to be drug related will be summarised separately. Separate tables will also be provided for subjects with SAEs, subjects with AESIs and subjects with other significant AEs (according to ICH E3 ([8](#))). AEs will also be summarized by maximum intensity.

The system organ classes will be sorted according to the standard sort order specified by the EMA, preferred terms will be sorted by total frequency (within system organ class).

For disclosure of AE data on ClinicalTrials.gov, the frequency of subjects with non-serious AEs occurring with an incidence of greater than 5 % (in preferred terms) will be summarised by treatment, primary system organ class and preferred term. The frequency of subjects with SAEs will also be summarised.

For disclosure of AE data in the EudraCT register, the frequency of AEs, the frequency of non-serious AEs with an incidence of greater than 5 % (in preferred terms) and the frequency of SAEs will be summarised.

For support of lay summaries, the frequency of subjects with drug-related SAEs will be summarised by treatment, primary system organ class and preferred term.

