7.8.2 Laboratory data

The analyses of laboratory data will be descriptive in nature and will be based on BI standard "Display and Analysis of Laboratory Data" ([7](#)) [001-MCG-157].

Descriptive statistics of laboratory values over time and for the difference from baseline (see [Section 6.7](#)) will be provided. Frequency tables of changes between baseline and last value on treatment with respect to the reference range will be presented.

The descriptive summary table will be repeated for the treatment period 2 with the last assessment prior to loading RI defined as baseline. This summary will include the assessments during loading RI in addition to the BI 425809+RI on-treatment assessments.

Possibly clinically significant abnormal laboratory values are only those identified either in the Investigator's comments on the eCRF or at the RPM/DBLM at the latest. It is the Investigator's responsibility to decide whether a lab value is clinically significant abnormal or not. Standard or project-specific rules for flagging clinically significant values will not be applied in this study.

Clinically relevant findings in laboratory data will be reported as baseline conditions (at screening) or as AEs (during the trial) if judged clinically relevant by the investigator, and will be analysed as such.

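### Does leaving follow-up phases out of the main AE tables hide liver injury found after BI 425809 alone?

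*SAP*

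**What the plan says.** SAP Table 6.1: 1 is titled "Flow chart of analysis phases for statistical analysis of AEs, safety laboratory and vital signs". It ends the on-treatment phase for BI 425809 alone at "Minimum of date/time of first administration of BI 425809 + REP (11 days * 24 h) and first administration of loading RI". What follows, up to the first rifampicin dose, is the phase labelled F/U BI.

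For the AE displays in CTR Section 15 and Appendices 16.1.9.2.8.2 and 16.1.9.2.8.3, SAP 6.1 states: "Screening, follow-up and post-study periods will not be included in these sections/appendices". It then adds a display without that restriction: "CTR Appendix 16.1.9.2.8.1 displays will present results for the screening, on-treatment, follow-up and post-study phases", with a total over all study phases.

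SAP 7.8.1 says "Separate tables will also be provided for subjects with SAEs, subjects with AESIs and subjects with other significant AEs" and names no CTR section for them. The only AESI (CTP 5.2.2.1, repeated in SAP 7.8.1) is hepatic injury, defined by AST/ALT and total bilirubin limits.

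For laboratory data, SAP 6.1 presents results by treatment period. SAP 7.8.2 plans descriptive statistics over time and differences from baseline, and adds: "Frequency tables of changes between baseline and last value on treatment with respect to the reference range will be presented". A further summary covers period 2: "This summary will include the assessments during loading RI in addition to the BI 425809+RI on-treatment assessments". Its baseline, in SAP 6.7, is "the last follow-up assessment during treatment period 1 (i.e., lab value at Day 43").

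**The concern.** A laboratory-defined event can be found only when blood is tested. If the on-treatment window after BI 425809 alone contains no scheduled liver test, an asymptomatic case could not be counted in that column, in the total over the two BI 425809 phases, or in the on-treatment total. A zero there would then say more about the sampling schedule than about the drug. The two columns involving rifampicin appear to contain scheduled tests (Day -3 and 72 h in the flow chart), so the columns would differ in their chance of detecting a case. The same reasoning suggests that the table of changes to the last on-treatment value would have no scheduled post-dose entry for BI 425809 alone. At stake would be a falsely reassuring safety table for the reference treatment.

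**Working it through.** **Timing.** The inputs are the REP of 11 days (CTP 5.2.2.2, SAP Table 6.1: 1), Day 43 at 1008 h with a window of +/- 3 h (CTP Flow Chart), at least 49 days between BI 425809 doses (CTP 4.1.4), and the first rifampicin dose at -134 h (CTP Flow Chart).

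- End of the on-treatment phase: 11 x 24 = 264 h, as in the SAP.
- Earliest second BI 425809 dose: 49 x 24 = 1176 h. Earliest rifampicin dose: 1176 - 134 = 1042 h. This is later than 264 h, so the REP sets the end of the phase.
- Day 43: (43 - 1) x 24 = 1008 h, or 1005 to 1011 h with the window. That is 741 to 747 h after the phase closes and nominally 1042 - 1008 = 34 h before the earliest rifampicin dose. The visit lies in F/U BI.
- Of the minimum 1042 h, 264 h (25.3%) is on treatment and 1042 - 264 = 778 h (74.7%) is follow-up. These are shares of calendar time and do not measure risk.

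The timing behind the concern is therefore right.

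**Is there really no liver test before 264 h?** The likeliest reading of the flow chart says so, but the extracted table has lost its column alignment. Rows from 34 h to 264 h show two leading marks, which would fit PK plus metabolite sampling. The Day 43 row also shows two leading marks, and SAP 6.7 confirms a laboratory value on that day. Two marks therefore do not exclude a laboratory test. Day 15 (336 h, 72 h after the phase ends) has a third mark and is probably a laboratory visit, but this too is inferred.

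**Is the AE allocation a departure from the protocol?** CTP 5.2.2.2 treats events up to the end of the REP as on treatment and later ones as post-treatment. CTP 7.3.3 gives events between the REP and the next intake a category of their own, which SAP 4 renames follow-up. Table 6.1: 1 applies exactly this. An event with onset about 31 days after the REP (741/24 = 30.9) belongs outside the on-treatment column by the protocol's own definition.

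**Where would a Day 43 case be seen?**

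| Display | Shown? |
|---|---|
| Section 15, BI 425809 column and on-treatment totals | No, if onset is recorded at the sample date |
| Appendix 16.1.9.2.8.1, follow-up phase and all-phase total | Yes |
| Separate AESI listing (CTP 7.3.3) | Yes |
| Discussion of discontinuations in the CTR (CTP 3.3.4.1), if the subject is removed | Yes |

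**Laboratory tables.** Three statements fit together. SAP 6.1 shows laboratory results by treatment period, CTP 6.2.2 defines period 1 as Days 1 to 43, and SAP 6.7 places the Day 43 value within treatment period 1. On that reading the value belongs in the period 1 displays. The descriptive statistics over time are in any case planned separately from the table of changes to the last on-treatment value.

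**The case for a change.** The strongest case for the concern is comparability. The protocol wants treatments compared descriptively, yet one column may have no scheduled liver test while the others have at least one. If all 16 subjects were tested, 0/16 would give a one-sided 95% upper bound of 1 - 0.05^(1/16) = 17.1%. If nobody were tested, it would give no bound. The SAP prints no number tested that would tell these apart. The wording on the last on-treatment value is also loose: SAP 6.1 says treatment period but reuses the phase labels, and SAP 7.8.2 speaks of on-treatment assessments. Finally, CTP 7.3.3 contains one sentence that assigns events up to the next intake to the preceding treatment, which would put a Day 43 case under BI 425809.

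Some of this stands. The wording in 7.8.2 could be tighter, and an on-treatment zero should not be read as evidence from scheduled testing. The rest does not carry the concern:

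- The sentence in CTP 7.3.3 is followed at once by the REP-based rule, which agrees with 5.2.2.2, and the section leaves the detailed intervals to the TSAP.
- The window is not without observation. AE questioning runs through it, and CTP 5.2.2.1 requires liver tests, unscheduled if necessary, when symptoms of hepatic injury appear.
- Technical details are referred to the ADS Plan and the sponsor's laboratory standard, which are not available here, so an omission in the laboratory tables is not shown.
- That the AESI table stands in Section 15 is an inference. If it belongs to Appendix 16.1.9.2.8.1, follow-up is already included.

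**Conclusion.** The concern does not hold. Its arithmetic is correct: the phase closes at 264 h and the Day 43 test at 1008 h falls in follow-up. But the allocation is the protocol's own REP rule, and the SAP already plans a display by phase that includes follow-up and an all-phase total. The laboratory data have a consistent reading that keeps Day 43 in period 1.

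The largest effect is one of placement. A single case among 16 subjects (1/16 = 6.25%) would appear under follow-up and not under BI 425809. Even that requires three things: onset recorded at the sample date, the AESI table placed in Section 15, and no liver test before 264 h, which the damaged flow chart suggests but cannot prove. The AE and laboratory analyses are descriptive, and no PK estimate, decision or safety action depends on this point. Extra columns or a row for the number tested would be a matter of presentation preference.

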6.2 IMPORTANT PROTOCOL VIOLATIONS

Data discrepancies and deviations from the CTP will be identified for all subjects in the database (i.e., treated subjects). Consistency check listings (for identification of violations of time windows) and a list of protocol deviations (e.g. deviations in drug administration, in blood sampling times, etc.) will be provided to be discussed at the RPM/DBLM. At this meeting, it will be decided whether a discrepant data value can be used in analyses or whether it must be corrected in the clinical database. Each protocol deviation must be

assessed to determine whether it is an IPV. For definition of IPVs, and for the process of identification of these, refer to the BI reference document "Protocol Violation Handling Definitions" ([2](#)) [001-MCS-50-413 RD-01].

If any IPVs are identified, they are to be summarised into categories and will be captured in the RPM/DBLM minutes via an accompanying Excel spreadsheet ([3](#)) [001-MCS-50-413_RD-02]. The following table contains the categories which are considered to be IPVs in this trial. If the data show other IPVs, this table will be supplemented accordingly by the time of the RPM/DBLM.

IPVs will be summarised and listed.

Table 6.2: 1 Important protocol violations

Category / Code	Description
A	Entrance criteria not met
A1	Inclusion criteria violated
A2	Exclusion criteria violated
B	Informed consent
B1	Informed consent not available
B2	Informed consent too late
C	Trial medication and randomisation
C1	Incorrect trial medication taken
C2	Incorrect dose of trial medication taken
C3	Non-compliance
C4	Incorrect intake of trial medication
C5	Improper washout between treatments
D	Concomitant medication
D1	Prohibited medication use
E	Missing data¹
None	
F	Incorrect timing
F1	Certain violations of time schedule used to measure primary or secondary data ²
G	Other trial specific important violations
G1	Certain violations of procedures used to measure primary or secondary data
G2	Incorrect intake of meal

Violations C1, C2, C4, G1 and G2 can only be detected at the trial site.

¹ Missing visits, evaluations, and tests will be considered missing data, not PVs
² Time 1 visit will be 1.1 for 1. IPV and 1 visit for 0.1

² Time deviations will only be flagged as IPV, when leading to exclusion of the entire subject from and analysis set. See the PI for a detailed description of the IPV and how it is defined. [C] [S01, MCS 56-413, RD 011]

Source: BI reference document 'Protocol Violation Handling Definitions' (2) [001-MCS-50-413_RD-01].

6.3 SUBJECT SETS ANALYSED

All entered subjects who received study medication will be included in the safety analysis and in the PK analysis depending on the availability of measurement values, and on their adherence to the CTP. The analysis sets are defined as follows:

- **Entered set (ES):**
This subject set includes all entered subjects, whether treated or not.
It will be used for analysis of disposition.
- **Treated set (TS):**
This subject set includes all subjects from the ES who were documented to have received at least one dose of study drug. This is the full analysis set population in the sense of ICH-E9. It will be used for analysis of safety, demographic data, baseline characteristics, and disposition.
- **PK analysis set (PKS):**
This subject set includes all subjects from the TS who provided in any period at least one primary or secondary PK endpoint value that is judged as PK evaluable and is not affected by PVs relevant to the statistical evaluation of PK endpoints. Thus, a subject will be included in the PKS, even if he contributes only one PK endpoint value for one period to the statistical assessment. Whether a PK endpoint is evaluable or a PV is relevant will be decided no later than at the RPM.
This subject set will be used for the analysis of BA.

CTP: *Relevant protocol violations may be:*

- *Incorrect trial medication taken, i.e. the subject received at least one dose of trial medication the subject was not assigned to*
- *Incorrect dose of trial medication taken*
- *Use of restricted medications*

A PK endpoint value will be considered as non-evaluable, if for example:

- *The subject experiences emesis at or before two times median t_{max} . Median t_{max} is to be taken either from the median t_{max} for the reference product or from median t_{max} for the test product, depending on whether the subject had experienced emesis after taken the test or the reference product. Median t_{max} is to be determined excluding the subjects experiencing emesis.*
- *The subject has a protocol deviation relevant to the evaluation of relative bioavailability*
- *Use of restricted medications*

Violations may lead to exclusion of single measurements or parameters for a subject or even to exclusion of all data of the subject.

Excluded subjects will be listed with their individual plasma concentrations and individual pharmacokinetic parameters, however, will not be included in descriptive statistics for plasma concentrations, pharmacokinetic parameters or other statistical assessments.

The discussion of all exceptional cases and problems and the decisions on the allocation of subjects to populations will be made at latest at the RPM/DBLM.

Table 6.3: 1 Subject sets analysed

Class of endpoint	ES	TS	PKS	Subject set
Disposition	X	X		
IPVs	X			
Demographic/baseline endpoints	X ¹	X		
Exposure		X		
Safety parameters		X		
Primary PK endpoints			X	
Secondary PK endpoint			X	

[†] only summary of country and age for disclosure in the EudraCT register

6.5 POOLING OF CENTRES

This section is not applicable, because the study was performed in only one centre.

6.6 HANDLING OF MISSING DATA AND OUTLIERS

Data of screened subjects who were withdrawn from the trial prior to first administration of trial medication will not be reported in the CTR.

Data of subjects who failed to complete all periods of the study (dropouts or withdrawals) will be reported in the CTR as far as their data are available. All withdrawals will be documented and the reason for withdrawal recorded in the CTR.

CTP: *With respect to safety evaluations, it is not planned to impute missing values.*

The only exception where imputation might be necessary for safety evaluation are AE dates. Missing or incomplete AE dates are imputed according to BI standards ([4](#)) [001-MCG-156_RD-01].

Missing data and outliers of PK data are handled according to BI standards ([5](#)) [001-MCS-36-472_RD-01]. **CTP:** *Drug concentration data identified with NOS (no sample available), NOR (no valid result), NOA (not analysed), BLQ (below the lower limit of quantification), or NOP (no peak detectable) will be displayed as such and not replaced by zero at any time point (this rule also applies also to the lag phase, including the predose values).*

CTP: *For the non-compartmental analysis, concentration data identified with NOS, NOR or NOA will generally not be considered. Concentration values in the lag phase identified as BLQ or NOP will be set to zero. All other BLQ/NOP values of the profile will be ignored. The lag phase is defined as the period between time zero and the first time point with a concentration above the quantification limit.*

6.7 BASELINE, TIME WINDOWS AND CALCULATED VISITS

Baseline for the evaluation of data of the “BI 425809+RI” treatment period will be defined as the last available value at Visit 3 before the second BI 425809 dose.

For an additional laboratory summary, baseline of treatment period 2 (“Loading RI” plus “BI 425809+RI”) is defined as the last follow-up assessment during treatment period 1 (i.e., lab value at Day 43).

Time windows are defined in Section 6.1 of the CTP. Adherence to time windows will be checked at the RPM/DBLM.

7. PLANNED ANALYSIS

The format of the listings and tables will follow the BI guideline "Reporting of clinical trials and project summaries" ([9](#)) [001-MCG-159].

The individual values of all subjects will be listed, sorted by subject number and visit. AE listings will be sorted by assigned treatment (see [Section 7.8.1](#) below for details). The listings will be contained in Appendix 16.2 (SDL) of the CTR.

The following standard descriptive statistical parameters will be displayed in summary tables of continuous variables:

N	number of non-missing observations
Mean	arithmetic mean
SD	standard deviation
Min	minimum
Median	median
Max	maximum

For plasma concentrations as well as for all PK parameters, the following descriptive statistics will additionally be calculated:

CV	arithmetic coefficient of variation
gMean	geometric mean
gCV	geometric coefficient of variation

The data format for descriptive statistics of concentrations will be identical with the data format of the respective concentrations. The descriptive statistics of PK parameters will be calculated using the individual values with the number of decimal places as provided by the evaluation program. Then the individual values as well as the descriptive statistics will be reported with three significant digits in the CTR.

Tabulations of frequencies for categorical data will include all possible categories and will display the number of observations in a category as well as the percentage (%) relative to the respective treatment group. Percentages will be rounded to one decimal place. The category missing will be displayed if and only if there are actually missing values. Percentages will be based on all subjects in the respective subject set whether they have non-missing values or not.

